#### (2) Doppler ultrasound parameters:

1) Deceleration time EDT of mitral valve E peak, A peak, E/A peak and E peak;

2) s', e 'and a' at the interventricular septum of mitral annulus;

3) s', e 'and a' at the lateral wall of mitral annulus;

4) E peak and A peak of tricuspid valve;

5) s', e ', a' at the lateral wall of tricuspid annulus;

6) Left ventricular Tei index: the ratio of the sum of left ventricular isovolumic systolic time (ICT) and isovolumic diastolic time (IRT) to ejection time (ET);

7) Right ventricular Tei index: the ratio of the sum of right ventricular isovolumic systolic time (ICT) and isovolumic diastolic time (IRT) to ejection time (ET).

#### (3) Relevant parameters of two-dimensional speckle tracking:

1) Segmental longitudinal strain and strain rate of 17 segments of left ventricular myocardium, and global longitudinal strain and strain rate;

2) Segmental circumferential strain and strain rate, global circumferential strain and strain rate of 17 segments of left ventricular myocardium;

3) Segmental radial strain and strain rate, global radial strain and strain rate of 17 segments of left ventricular myocardium;

4) Left ventricular bottom angular displacement, apex angular displacement, myocardial torsion torque;

5) The longitudinal strain of the intima and adventitia of 17 segments of left ventricular myocardium, and global longitudinal strain of the intima and adventitia;

6) The circumferential strain of the intima and adventitia of 17 segments of left ventricular myocardium, and the circumferential strain of global intima and adventitia;7) The radial strains of the intima and adventitia of 17 segments of left ventricular myocardium, and global radial strains of the intima and adventitia;

#### (4) Myocardial work parameters:

According to the patient's blood pressure, left ventricular outflow tract spectral Doppler image, apical four chamber heart, apical two chamber heart, and apical three chamber heart section dynamic images, the pressure strain loop (PSL) is obtained by offline analyzing and calculating with Echopac software. Then the global work index (GWI), global constructive work (GCW), global wasted work (GWW), global work efficiency (GWE) and other indicators are obtained.

(5) The left ventricular remodeling parameters required in this study are calculated from the above obtained ultrasound parameters as follows:

LVM=0.8×1.04×[(IVSTd+LVEDD+LVPWTd)-LVEDD]+0.6

RWT =(LVPWTd×2)/LVEDD

#### (6) Cardiac morphological changes:

Record whether there is pericardial effusion (small, medium and large) and pericarditis during follow-up, and whether there is mitral valve, tricuspid valve, aortic valve, pulmonary valve and other valve diseases, such as valve sclerosis, stenosis, etc. When each valve has regurgitation or stenosis, note the peak flow rate, peak pressure difference and average pressure difference, especially tricuspid regurgitation;

## (7) Three-dimensional ultrasound parameters:

Echopac software and QLAB software were used to analyze the retained threedimensional images to obtain three-dimensional left ventricular volume parameters, three-dimensional left ventricular ejection fraction, three-dimensional left ventricular strain, three-dimensional left atrial volume parameters, three-dimensional left atrial strain parameters, three-dimensional right ventricular volume parameters.

[figure not shown]
#### (8) Carotid ultrasound parameters:

Diameters, blood flow velocities and plaques and shear force strains of the common carotid artery, internal and external carotid arteries, and bifurcation.

## (9) Development of artificial intelligence analysis software:

Using the images of hypertensive population collected by the project, we would measure, analyze and calculate to collect the two-dimensional, three-dimensional, Doppler, strain, work and remodeling parameters of hypertension. Combining with the artificial intelligence technology, we will establish an ultrasonic data bank of Chinese hypertensive population. Meanwhile, we will compare the data with the EMINCA database of Chinese healthy adults, and use machine learning methods to build an artificial intelligence measurement module. The combination of ultrasonic dynamic image and neural network algorithm can achieve the rapid, dynamic and real-time evaluation of the cardiac structure and function of hypertension, automatically measure and identify normal and abnormal thresholds, and help hypertensions get more accurate diagnosis, evaluation and treatment.

## **DIAGRAM OF RESEARCH SCHEME**

## **CHART OF RESEARCH SCHEME**

Follow-up time	0 month	12th month	24th month	36th month	48th month
Information	•				
Medical history	•				
Inclusion Criteria	•				
Informed consent	•				
Electrocardiogram	•	•	•	•	•
Physical examination	•	•	•	•	•
Laboratory examination	•				
Echocardiography	•		•		•
Arterial ultrasound	•		•		•
Drugs treatments	•	•	•	•	•
Adverse events		•	•	•	•

#### **ETHICS**

 In the process of clinical research, the personal rights and interests of the subjects must be fully guaranteed, and the reliability of the research must be ensured. The rights, safety and health of subjects must be higher than the consideration of scientific and social interests.
The research scheme can only be implemented after being reviewed, agreed and signed by the Ethics Committee. During the study, any modification of the study protocol shall be approved by the Ethics Committee.

(3) The investigator or its designated representative must explain the details of the clinical study to the subject, and obtain the informed consent after fully explained the study.

(4) Informed consent of the subject (see the Informed Consent Form for details).

Before each patient is enrolled in this study, the physician has the responsibility to completely and comprehensively introduce the purpose, procedure, possible benefits and risks of this study to him or his designated representative in written form. Patients should be made aware of their right to withdraw from the study at any time. Before enrollment, each patient must be given a written informed consent form (included in the protocol in the form of appendix) so that the subject can understand and agree. Only after signing the informed consent form voluntarily, they could be included in the clinical trial. The informed consent form will be kept as one of the original data of the clinical trial for future reference.

#### **ELECTRONIC DATA MANAGEMENT (eCDM)**

This test adopts the electronic data management system (DAS for eCDM).

(1) Construction of electronic case report form (eCRF): the data administrator constructs eCRF according to the research scheme and research medical record.

(2) Permission allocation: The data administrator creates accounts and grants different permissions to access eCDM according to different identities of main research center, supervisor, inspector, etc. If the researchers in each center can only see the contents of the center and have the right to modify the data, the main research centers are limited to browsing all cases; The monitors and auditors can read the case information of each center, but they have no authority to modify the data, but they can insert comments or questions.

(3) Data entry: clinical investigators or data entry personnel designated by researchers

timely and accurately enter the data in the study medical records into eCRF. eCRF is not used as the original record, and its content is derived from the "study medical record".

(4) Data questions and answers: The supervisor conducts the audit through eCDM, and raises questions online at any time when problems are found. The researcher will answer the questions online, correct the wrong data, and if necessary, the supervisor can repeat the questions.

(5) Data locking and export: after each subject completes the test and is checked by the supervisor, the data administrator will lock the data until the last subject's data is locked. After all the data are locked, the data administrator will import them into the designated database and submit them to the statisticians for statistical analysis.

6. After the study ends, eCRF was printed and archived as required. The data management center will keep the electronic data until 5 years. During this period, if SFDA needs to audit, the data management center can open the system at any time after making an appointment.

## STATISTICAL TREATMENT

#### (1) Analysis data set

Full analysis set (FAS): the patient enrolled according to the principle of Intention To Treat (ITT), and the data composed of all enrolled hypertensive patients. The patients who failed to observe adverse cardiovascular and cerebrovascular events were treated as deletion and carried outsides in the last follow-up date.

PPS: refers to the cases that meet the inclusion criteria but do not meet the exclusion criteria, and the cases that meet the test protocol and complete the CRF requirements are analyzed (PP analysis).

#### (2) Statistical methods

#### **Demographic Analysis**

1) Measurement data: mean, standard deviation, median, maximum, minimum and quartile are used for description;

2) Counting data: described by frequency and composition ratio.

## (3) Group analysis:

1) For the healthy volunteers and hypertensive patients enrolled in the group: between 9:00

a.m. and 17:00 p.m. on the day of enrollment, at an interval of more than 4 hours, the patients performed two echocardiographic examinations in a calm state, measured and recorded their blood pressure at the same time (three measurements at an interval of 1-2 minutes), and measured the indicators at the two baseline levels on the day of enrollment. The changes of left ventricular global longitudial strain (GLS) and myocardial work (MW) in hypertension and healthy volunteer were compared, and the correlation between them and the changes of blood pressure was analyzed;

2) Analysis for hypertensive patients with different left ventricular configurations: configuration analysis was conducted based on the left ventricular remodeling standards recommended by ASE/EACVI 2015 guidelines and the EMINCA study combined with Ganau classification. Hypertensive patients were divided into normal left ventricular configuration group, left ventricular remodeling group, left ventricular eccentric hypertrophy group and left ventricular concentric hypertrophy group. Baseline, 12months, 24months, 36months and 48months echocardiography images were recorded and analyzed, compared the cardiac structure and functional indicators, and recorded clinical adverse events;

(2) Analysis for hypertensive patients with different left atrial configurations: according to the abnormal threshold of left atrial enlargement recommended by ASE/EACVI 2015 guidelines and the standard of Chinese left atrial enlargement recommended by EMNICA study, hypertensive patients were divided into normal left atrial group and left atrial enlargement group. Baseline, 12months, 24months, 36months and 48months echocardiography images were recorded and analyzed, compared the cardiac structure and functional indicators, and recorded clinical adverse events.

#### (4) Analysis of main endpoint events:

1) Cox regression was used to analyze the predictive value of different types of left ventricular remodeling and left atrial enlargement on adverse cardiovascular events. ROC analysis was used to compare the incremental effect of left ventricular remodeling, left ventricular hypertrophy and left atrial enlargement on the predictive ability of hypertensive cardiovascular events; NRI [net corrected classification, i.e. (new sensitivity + new specificity) - (old sensitivity + old specificity)] was used to evaluate and compare the ability

of left ventricular remodeling, left ventricular hypertrophy and left atrial enlargement to re stratify and optimize the risk of cardiovascular events in hypertension. Multivariate regression analysis was used to analyze the factors affecting left ventricular remodeling and left atrial enlargement in hypertension.

2) The incidence time of adverse cardiovascular events was stratified by left ventricular remodeling, left ventricular hypertrophy and left atrial enlargement. Cox regression analysis was used to calculate the hazard ratio and its bilateral 95% confidence interval of different influencing factors.

(5) Statistical software: SAS 9.4 or SPSS software was used for analysis. Bilateral tests were used for statistical tests.  $P \le 0.05$  were considered statistically significant.

(6) Interim analysis: No interim analysis will be conducted in this study. If special cases occur, the main research center, researchers and statistical experts will discuss and decide.

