## **EFFICACY ASSESSMENT**

Primary study endpoints: emerging atrial fibrillation, transient ischemic attack (TIA) or stroke, unstable angina, myocardial infarction, heart failure, coronary revascularization, cardiovascular death; Secondary study endpoints: decreased cardiac function with preserved ejection fraction; new cardiac remodeling; aortic aneurysm or aortic dissection; ECG showed that QTc (QT interval corrected by heart rate) was more than 500ms or QTc was longer than the baseline level for more than 60ms, emerging torsade de pointes ventricular tachycardia and other serious arrhythmias; the relationship between the deviations of blood pressure within the same day and the difference of cardiac function indexes.

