#### **RESEARCH PLAN**

#### **Estimation of Sample Size**

Use PASS 11.0.7 software, bilateral inspections,  $\alpha = 0.05$ , with the incidence rate of cardiovascular adverse events in the left ventricular hypertrophy group was 4.9%, and the incidence rate of cardiovascular adverse events in the left ventricular non-hypertrophy group was 2.2%, at least 986 hypertensive patients were included in the left ventricular hypertrophy group and the left ventricular non hypertrophy group, respectively. Considering the 10% loss rate, at least 1085 patients were included. With 20 research centers, we planned to collect at least 110 patients with hypertension (including 55 patients in left ventricular hypertrophy group), 5-10 healthy volunteers (aged 30-60 years) in each center. Then 2200 patients with hypertension in total, and 100 healthy volunteers will be selected in this study.

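### The study is sized for one contrast (LVH v non-LVH), but the main analysis names no primary contrast, standard or composite and judges everything at P ≤ 0.05

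*Protocol*

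**What the plan says.** **Sample size** (Protocol, Estimation of Sample Size). The calculation uses "bilateral inspections" at α = 0.05. The assumed incidences are "cardiovascular adverse events in the left ventricular hypertrophy group was 4.9"% and "cardiovascular adverse events in the left ventricular non-hypertrophy group was 2.2"%, with no period given. The result is that "at least 986 hypertensive patients were included in the left ventricular hypertrophy group and the left ventricular non hypertrophy group, respectively". After loss: "Considering the 10% loss rate, at least 1085 patients were included". Twenty centres each enrol at least 110 hypertensive patients, 55 of them with LVH, for 2,200 in total. The section does not say which standard defines LVH for this quota.

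**Groups** (Protocol, Groups; Statistical Treatment (3)). Patients are classified into four left ventricular geometries, normal (NG), concentric remodelling (CR), eccentric hypertrophy (EH) and concentric hypertrophy (CH), and into two left atrial groups. Both classifications are made under ASE/EACVI 2015 and again under EMINCA.

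**Main analysis** (Statistical Treatment (4) and (5)). "Cox regression was used to analyze the predictive value of different types of left ventricular remodeling and left atrial enlargement on adverse cardiovascular events". ROC and NRI then compare remodelling, LVH and left atrial enlargement. Results at P ≤ 0.05, two-sided, "were considered statistically significant". No contrast is ranked above another.

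**Endpoint** (Efficacy Assessment). "Primary study endpoints: emerging atrial fibrillation, transient ischemic attack (TIA) or stroke, unstable angina, myocardial infarction, heart failure, coronary revascularization, cardiovascular death". The list is not described as a composite. The follow-up section (indicators of the first follow-up) gives a different list of adverse cardiovascular events to record.

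**The concern.** The Objectives section asks how different cardiac configurations relate to events, the sample size answers only the LVH question, and the main analysis sets several exposures and two standards side by side. Followed as written, a significant result for any exposure under either standard could be reported as the main finding. A contrast with few events could likewise be reported as showing no predictive value. Which contrast, standard and endpoint are primary belongs in a protocol, and here the objective, the sizing and the analysis do not settle on the same answer.

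**Working it through.** **1. The plan's own figure.** Pooled two-proportion formula, p1 = 0.049, p2 = 0.022, mean 0.0355, two-sided 0.05. Power is not stated, so 90% is tried:

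n = [1.96·√(2·0.0355·0.9645) + 1.2816·√(0.049·0.951 + 0.022·0.978)]² / 0.027² = (0.5129 + 0.3345)² / 0.000729 ≈ 985 per group.

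The protocol has 986, where power is 90.03%; 80% power would need only 737. The figure therefore belongs to LVH v non-LVH at 90% power. The 1,085 is 986 × 1.10, while 986/0.90 gives 1,096. The planned 1,100 per group covers either and leaves 1,100 × 0.90 = 990 after loss.

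**2. The two standards define different LVH groups.** The LVMI cut-offs are 115 (men) and 95 g/m² (women) under ASE/EACVI, and 108 and 99 under EMINCA.
- Men above 108 and up to 115 have LVH only under EMINCA.
- Women above 95 and up to 99 have LVH only under ASE/EACVI.

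LVH v non-LVH is thus two different tests, and the quota could be filled under either.

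**3. The two event lists differ.** The follow-up list omits atrial fibrillation, TIA and coronary revascularization, all three of which are primary in Efficacy Assessment. It adds aortic aneurysm or dissection, which Efficacy Assessment makes secondary. The event in the Cox model could follow either list.

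**4. False-positive rate.** Assume one composite and five contrasts per standard: LVH; CR, EH and CH each against NG; and left atrial enlargement. Two standards give ten tests.
- If independent: 1 − 0.95¹⁰ = 40%.
- Simulation with no marker related to events: 1,980 patients, 3.55% events, normally distributed markers, left atrial size correlated 0.5 with LV mass. With LV mass under the two standards correlated 0.99, 0.95 and 0.90, at least one P ≤ 0.05 occurs in 27.9%, 28.0% and 29.9% of studies.
- Separate simulation: 2,200 patients; LVMI 115 (SD 25) in men and 95 (SD 22) in women, RWT 0.43 (SD 0.08), LAVI 31 (SD 8), correlations 0.1-0.4. Ten tests give 28.5%, and five tests under one standard 17.5%. A further run gave about 27%.

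The marker distributions are assumptions; the protocol gives none. ROC and NRI are not counted.

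**5. Power inside the non-LVH group (CR v NG).** At 80% power and an equal split, detectable HR = exp[2.80/√(events × 0.25)].
- Rates as 48-month risks, before loss: 1,100 × 0.022 = 24.2 events, HR 3.1.
- Rates as 48-month risks, after loss: 990 × 0.022 = 21.8 events, HR 3.3. Power at HR 2.0 is 37%.
- Annual rates: 990 × [1 − 0.978⁴] = 990 × 0.0851 = 84 events, HR 1.8. Power at HR 2.0 is 89%.

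**6. Other contrasts, for balance** (48-month reading, after loss).
- Left atrial enlargement at 4.9% v 2.2%: 78% power at 20% prevalence, 86% at 30%, about 90% at 40-50%.
- EH v CH, equal split, 990 × 0.049 ≈ 48 events: 67% at HR 2.0, 80% at HR 2.25.

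**The case against.** This is an observational prognostic cohort whose purpose includes comparing standards and configurations. A multiplicity procedure such as Holm or fixed-order testing commonly sits in a SAP, which is not at hand, so its absence is no finding. The main analysis already plans hazard ratios with 95% confidence intervals, and ROC and NRI are presented as comparisons of predictive ability. The count of ten is also an assumption: the protocol does not specify pairwise class tests, and a four-level factor could be tested globally. All of this stands, and it limits the point to the missing primary contrast, standard and endpoint.

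Four stronger readings are tempting, but the protocol does not support them.
- **Each of the seven endpoints is tested at P ≤ 0.05.** No section says so. The sample size uses one overall rate, and the Cox text treats events collectively. The documented fault is only that the list is not called a composite.
- **The segmental strain values join the same family of tests.** They are listed as measurements, with no planned test against events.
- **A false positive is likely.** At 27-30%, or even 40%, it is well above 5% but not more likely than not.
- **Most contrasts are uninformative.** Left atrial enlargement has 78-90% power at the design rates. Power for the class contrasts depends on class sizes, hazard ratios and the unstated period of the rates.

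**Conclusion.** The concern holds in limited form. Only LVH v non-LVH is sized, yet nothing in the protocol makes it the primary test, fixes the standard that defines it, or states that the seven events form one composite. On one composite with ten contrasts, the false-positive risk is about 27-30% under the assumed distributions and 40% under independence, against a nominal 5%. The weakness of CR v NG is conditional: marked if the planning rates are 48-month risks (HR of about 3.1-3.3 needed at an equal split), much less so if they are annual (about 1.8). The change is worth making, but the sample size for the LVH contrast is not in question.

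**What to change.** - **Primary test.** In Efficacy Assessment, Estimation of Sample Size and Statistical Treatment (4), name Cox regression for LVH v non-LVH as the single primary test at two-sided 0.05. The endpoint is time to first event of the Efficacy Assessment list, stated to be a composite.
- **Standard.** Name the one standard that defines LVH for both the quota and this test. Which one is the sponsor's choice, to be fixed before outcome data are analysed.
- **Event list.** Align the follow-up list with the composite, so that every component is recorded.
- **Everything else.** Label the other standard, left atrial enlargement, the four-class contrasts, ROC and NRI as secondary or exploratory, reported as estimates with 95% confidence intervals.
- **Rates.** State the period to which 4.9% and 2.2% refer, and add that a null CR v NG result is not evidence of no effect.

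The cost is wording, and fewer results can be called confirmatory. The 986 per group and 90% power are kept. By comparison, Bonferroni over ten contrasts would cut power for LVH to 67% at 986 per group, or need 1,568 per group to restore 90%.

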Echocardiography is a commonly used clinical examination method, with ease of operation, safety, non-invasive, real-time imaging, strong repeatability, low cost and so on, which is widely used to evaluate the structure and function of the heart and cardiac hemodynamics. Framingham et al. found that there is a strong correlation between LVM detected by echocardiography and the incidence rate and mortality of cardiovascular diseases, and LVM is also the most commonly used tool for clinical diagnosis of left ventricular diastolic dysfunction (LVDD).

The LVM and LAV derived from the normal value data of Chinese healthy adults have been reported to be different from the recommended reference values in guidelines, and the distribution characteristics of hypertension remodeling are also different. However, this difference still lacks of large multi-center research to further confirm it. Meanwhile, the characteristics and outcomes of cardiac remodeling in Chinese hypertensive population and whether this difference in configuration has an impact on the treatment, prognosis and cardiovascular events of hypertensive population are still needed to be explored.

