#### **OBJECTIVES:**

This study was to observe the relationship between blood pressure and cardiovascular remodeling evaluated by different standards in hypertensive population; to compare the relationship between different cardiac configurations and cardiovascular events in Chinese hypertensive population.

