#### **RESEARCH DESIGN**

Studies have shown that different configurations of left ventricle and left atrial enlargement in hypertensive patients can predict the occurrence of cardiovascular events. The standards of left ventricular remodeling and left atrial enlargement based on European and American populations may not be applicable to Chinese populations. This study was a multicenter study to verify different left ventricular remodeling in Chinese hypertensive population, and explore the influence of different left ventricular remodeling standards on the treatment options and prognosis.

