## (1) Left ventricle remodeling groups: 2015 ASE/EACVI guideline standard:

Normal left ventricular geometry, NG: LVMI≤115g/m^2 (male) or LVMI≤95g/m^2 (female) and RWT≤0.42

Concentric remodeling, CR: LVMI $\leq 115$ g/m^2 (male) or LVMI $\leq 95$ g/m^2 (female) and RWT>0.42

Eccentric hypertrophy, EH: LVMI>115g/ m^2 (male) or LVMI>95g/ m^2 (female) and RWT $\leq$ 0.42

Concentric hypertrophy, CH: LVMI>115g/  $m^2$  (male) or LVMI>95g/ m2 (female) and RWT>0.42

Reference Values for Chinese (EMINCA) and Configuration Analysis Based on Ganau Typing:

Normal left ventricular geometry, NG: LVMI $\leq 108$ g/ m^2 (male) and RWT $\leq 0.51$  or LVMI $\leq 99$ g/ m^2 (female) and RWT>0.49

Concentric remodeling, CR: LVMI≤108g/ m^2 (male) and RWT>0.51 or LVMI≤99g/ m^2 (female) and RWT>0.49

Eccentric hypertrophy, EH: LVMI>108g/ m^2 (male) and RWT≤0.51or LVMI>99g/ m^2 (female) and RWT≤0.49

Concentric hypertrophy, CH: LVMI>108g/ m^2 (male) and RWT>0.51 or LVMI>99g/

 $m^2$  (female) and RWT>0.49

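### The EMINCA normal-geometry rule for women is printed the same as the concentric-remodeling rule, so the four EMINCA types do not partition women

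*Protocol*

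**What the plan says.** Protocol, Groups, (1) Left ventricle remodeling groups, defines four types by LVMI and RWT, once with ASE/EACVI 2015 cut-offs and once with EMINCA cut-offs. The types are normal geometry (NG), concentric remodeling (CR), eccentric hypertrophy (EH) and concentric hypertrophy (CH).

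For women under EMINCA, the NG line prints "LVMI $\leq 99$ g/ m 2 (female) and RWT>0.49". The CR line prints the same two conditions. The EH line prints "LVMI>99g/ m 2 (female) and RWT≤0.49".

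Statistical Treatment, (3) Group analysis, applies "the left ventricular remodeling standards recommended by ASE/EACVI 2015 guidelines and the EMINCA study combined with Ganau classification" to form the groups. It does the same for the left atrium with the two sets of atrial cut-offs, and records adverse events in the groups.

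Statistical Treatment, (4) Analysis of main endpoint events, then uses Cox regression on remodeling types and left atrial enlargement, states that "ROC analysis was used to compare the incremental effect of left ventricular remodeling, left ventricular hypertrophy and left atrial enlargement on the predictive ability", and adds an NRI. It names neither standard. Estimation of Sample Size sets 55 patients with left ventricular hypertrophy (LVH) among 110 hypertensive patients per centre, also without naming a standard.

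**The concern.** A four-type classification must put each patient in exactly one type. The printed EMINCA rules do not do this for women, and the error falls on NG, the type that would ordinarily serve as the reference in a four-group comparison.

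If the lines were coded as printed, the result would depend on the order of the code:

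- **NG tested first:** women with high RWT are labelled normal, and CR is empty for women.
- **CR tested first:** NG is empty for women.
- **Either order:** women with low LVMI and low RWT are missing.

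The same women do have a class under ASE/EACVI. The two standards would therefore be analysed in different sets of patients, which damages any comparison between them.

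**Working it through.** No sample-size arithmetic bears on the error, so the check is whether the printed rules form a partition.

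**Inputs** (Protocol, Groups, (1), EMINCA lines as printed)

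| Type | Men | Women |
|---|---|---|
| NG | LVMI≤108, RWT≤0.51 | LVMI≤99, RWT>0.49 |
| CR | LVMI≤108, RWT>0.51 | LVMI≤99, RWT>0.49 |
| EH | LVMI>108, RWT≤0.51 | LVMI>99, RWT≤0.49 |
| CH | LVMI>108, RWT>0.51 | LVMI>99, RWT>0.49 |

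**Test.** Take one patient in each cell, with LVMI low (80) or high (120) and RWT low (0.40) or high (0.60), and list every type whose conditions are met.

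| LVMI / RWT | Men, as printed | Women, as printed | Women, NG read as RWT≤0.49 |
|---|---|---|---|
| 80 / 0.40 | NG | none | NG |
| 80 / 0.60 | CR | NG and CR | CR |
| 120 / 0.40 | EH | EH | EH |
| 120 / 0.60 | CH | CH | CH |

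The men's rules give one type per cell. The women's rules fail in both cells with LVMI≤99. Reversing one sign in the women's NG line gives one type in every cell.

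**Which line is out of step.** For men, NG and CR share the LVMI condition and take opposite sides of the RWT cut-off. The women's EH and CH lines also take opposite sides of 0.49. Only the women's NG and CR lines take the same side. NG and EH should share the low-RWT condition, as they do for men (both ≤0.51). The women's EH line has ≤0.49 and the women's NG line has >0.49.

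**What the error does not reach.**

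- *Hypertrophy split.* EH and CH together are LVMI>99 in women and LVMI>108 in men, and RWT cancels out. LVH yes/no is unchanged if it is read from LVMI.
- *ASE/EACVI types.* These use RWT≤0.42 against >0.42 with LVMI 115 (men) and 95 (women). The printed lines partition both sexes.
- *Sample size.* This uses only LVH and non-LVH event rates of 4.9% and 2.2%, two-sided α=0.05. Power is not stated; 90% is inferred. n = [1.960·√(2·0.0355·0.9645) + 1.282·√(0.049·0.951 + 0.022·0.978)]² / 0.027² ≈ 985 per group, against 986 stated. No NG or CR quantity enters.

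**The case against.** **It is an obvious slip.** The intended sign can be recovered from the neighbouring lines, and a programmer building four exclusive groups would soon meet the overlap. This is fair, and it limits the likely harm. It does not make the printed rule usable: the line defines an analysis group, and two sections of the statistical plan rely on those groups.

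**It may be a reading error.** The text was taken from a PDF and the line mixes symbol styles, so a single misread sign cannot be excluded. This stands. It is a reason to check the source first.

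**A stronger reading is tempting.** Research Design aims to "explore the influence of different left ventricular remodeling standards on the treatment options and prognosis", and Background says that "whether this difference in configuration has an impact on the treatment, prognosis and cardiovascular events of hypertensive population are still needed to be explored". The endpoint section names no standard, and its NRI formula, "new sensitivity + new specificity) - (old sensitivity + old specificity", does not say what is old and what is new. A reader might infer that the plan cannot answer its own question about the standards and needs a prescribed paired contrast between them. The documents do not support going that far:

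- (3) Group analysis, in the same statistical section, already groups patients by both standards for ventricle and atrium. The natural reading is that the endpoint analyses follow both groupings.
- The Objectives tie the standards only to blood pressure and remodeling: "to observe the relationship between blood pressure and cardiovascular remodeling evaluated by different standards in hypertensive population". The link to prognosis is one exploratory clause in Research Design.
- The NRI reference model and the form of any confidence interval are commonly left to an SAP, which may exist but is not at hand. The endpoint section compares markers and speaks of incremental effect, which suggests a model with the marker against one without it. Setting old to ASE/EACVI and new to EMINCA would replace that comparison, not define it.

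A reader might also want the number of women affected. Any figure would rest on assumed sex, LVMI and RWT distributions, so none is given.

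**Conclusion.** Wrong as written, for one line only: the EMINCA normal-geometry rule for women. Applied as printed, it leaves all women with LVMI≤99 and RWT≤0.49 without a class and gives all women with LVMI≤99 and RWT>0.49 two classes. The EMINCA four-type groups, and the Cox, ROC and NRI results built on them, are then not validly defined for women.

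This conclusion needs no distributional assumption. It rests on the printed sign being the sign in the source document. The hypertrophy split stays intact as long as it is taken from LVMI and is not built up from the NG and CR lines.

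That the endpoint and sample-size sections name no standard is a matter of clarity, not an error.

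**What to change.** 1. **Groups, (1), EMINCA NG line.** Check the sign against the source PDF. If it is as shown here, reconcile the women's NG line with the protocol's own CR and EH lines, so that NG is the complement of CR: LVMI≤99 and RWT≤0.49.
2. **Minor: Statistical Treatment, (4).** Add a sentence that the endpoint analyses are run under both standards in the same patients, as (3) Group analysis implies.
3. **Minor: Estimation of Sample Size.** Name the standard that defines the LVH recruitment group.

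The cost is one corrected sign and two short clarifications, with no new data and no change to the sample size. The protocol requires Ethics Committee approval for modifications, so the three edits are best submitted together.
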